Because this is a cross-sectional design in which different patients are sampled at each step in the study, we do not need to include a random effects term for repeated measures on the same individuals. The effect size adjusted for calendar time and its 95% confidence interval will be calculated to assess the estimated change in outcomes after introduction of the intervention.

Although the primary analysis will be intention-to-treat, if necessary, we will include an analysis of what actually happened if the CBOCs do not crossover to the intervention at the original specified time.

Per Hemming et al.,⁸¹ we will report the estimated intra-cluster correlation for use in design of future trials. In addition, we will report the time effect from the fitted model to allow assessment of possible confounding effects of calendar time. We may include an effect modifier term in the model representing the length of the period up to the current observation during which the CBOC has been exposed to the intervention. This will allow examination of the way the impact of the Telemedicine Based care develops over time once introduced into the CBOC.

Power Calculation for Hypothesis 2. We calculated the sample size for the stepped wedge design following the approach of Woertman et al.,⁸⁶ which has been corrected by Hemming, Girling, and Taljaard.^{84, 87, 88}

We first determined the sample size needed if individuals were randomized (N_u). This is then multiplied by a design effect, DE_{sw} , to correct for both clustering and the stepped wedge design.

$$DE_{sw} = \frac{1 + \rho(tm + m - 1)}{1 + \rho(0.5tm + m - 1)} * \frac{3(1 - \rho)}{2(t - 1/t)}$$

where m is the number of subjects within a cluster in each measurement period, ρ is the intra-cluster correlation (ICC), t is the number of randomization steps, and k clusters are measured at each of T measurement periods. The required sample size for analysis using the stepped wedge design is then $N_{sw} = N_u * DE_{sw} * T$. Finally, we adjusted the required sample size formula to account for 20% attrition over the 6-month period to obtain the number of patients that need to be selected for assessment, N .

In our study, the 6 CBOCs will be randomly allocated two at a time to one of the $t = 3$ randomization steps. Based on earlier work, the intracluster correlation coefficient, ρ will be estimated as .01. There will be a total of 5 measurements for each cluster, including the control period(s), implementation, and maintenance period(s) (see schematic diagram). We assumed for the power calculations that approximately $m=18$ participants would be available within each CBOC in each 6-month time interval.

The calculations are based on having 80% power at a significance level of 0.05 to detect a medium effect size (Cohen's $d=0.42$) between the usual care referral model (EU) and the Telemedicine Blended model intervention group (TB) in our primary outcome measure for the effectiveness hypothesis, MCS from SF-12V. This represents a difference of 4 points in the MCS scores between the referral model group and the Telemedicine Blended Model group, assuming a pooled standard deviation of 10. This gives the unadjusted total sample size, N_u , of 128 for the two-sided, two-sample t-test of equal means.

The total number of patients to be selected for assessment across the 6 CBOCs will be 750. This was determined after adjusting the total sample size required under individual randomization N_u , for the design effect, multiplying by the 5 measurement periods, and accounting for a 20% attrition rate. This will result in approximately 600 patients providing baseline and 6-month follow-up data for analysis, accounting for attrition.

The assumption of approximately 18-30 participants at each CBOC in each 6-month period does not represent the maximum that can be recruited at a site in any six-month period; it is a possible average based on our experience in the first six-months of recruitment. We will recruit all eligible participants at the study sites as described elsewhere in the protocol.

Direct Access to Source Data/Documents:

Only authorized persons will have access to the information gathered in this study. Authorized persons may include regulatory agencies such as, the Government Accounting Office (GAO) or the Office for Human Research Protection (OHRP), Office of Research Oversight (ORO), as well as members of the Research Administration staff of CAVHS.

Data Safety and Monitoring Plan:

Although unlikely and unanticipated, a possible risk for this study is loss of confidentiality. All data will be managed to minimize the risk of loss of confidentiality. Consent forms and raw data forms will be stored in locked file cabinets in locked offices, or will be stored on the password protected VA computer network as appropriate. Study staff will only have access to the data they need for their work. Participants' names and contact information will not be included in the main study database nor in any datasets used for analysis. Instead, participants will be identified by study ID code only. A table linking participants' names with their study IDs will be stored in a separate database on the server. Only investigators and the research staff (including the study programmer) will have access to the key linking participants' names and study ID codes. The identifiers will be destroyed as early as possible as allowed by VA policies. All study databases will be stored on the secure VA network, not on local hard drives. Specifically, data will be stored on the HSR&D Service Drive at \\VHAV16FPC42.V16.MED.VA.GOV\PI Project Folders\[name]\Adapting and Implementing the Blended Collaborative Care Model in CBOCs. Data will also be stored on VA VINCI. The study protocol will be submitted to the CAVHS IRB and R&D Committee for approval before research begins.

Ethics:

This study will comply with principles of the Belmont Report. Ethical considerations specific to this study include the potential for loss of confidentiality. To avoid loss of confidentiality in any publication or other communication based on this data, no information specific enough to identify a participant will be included.

Data Handling and Recording:

Data will consist of questionnaires filled out by participants, qualitative data from interviews, and data extracted from the CDW. All data, other than CDW data extracts and required electronic enrollment logs, will be de-identified according to VHA policy for truly de-identifying data. All paper materials, including consent forms, will be stored in CAVHS building 58, rooms 105A or 254 (the private offices of the study coordinator and the PI) in a locked filing cabinet. Databases consisting of the data collected will be maintained in files on the password protected, secure VA HSR&D server \\VHAV16FPC42.V16.MED.VA.GOV (see above folder location) and VA VINCI. Removal of study access will be completed for research personnel when they are no longer part of the research team. Records will be retained indefinitely until the VA RCS has been revised regarding disposition of research records. VA approved methods will be utilized to destroy data when permitted.

If, in spite of the implemented precautions, participant data is lost, stolen, or compromised, it will be reported immediately to the PI. The PI or designee will report the event to the IRB, the ISO, the PO, and the ACOS/R&D as soon as possible, but no longer than 1 hour after learning of the breach of confidentiality.

References:

- 1 Williams JW, Jr., Gerrity M, Holsinger T, Dobscha S, Gaynes B, Dietrich A. Systematic review of multifaceted interventions to improve depression care. *General Hospital Psychiatry*. 2007; 29(2):91-116.
- 4 About the Office of Rural Health. http://www.ruralhealth.va.gov/about_orh.asp.

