Patient Recruitment: We will initiate recruitment at all sites 3 months into the first 6-month study period (labeled as “Identify Model” in the diagram above), during the implementation planning for Sites A and B. We will complete recruitment 3 months before the data analysis period begins. Thus, Veteran follow up will extend into the first 3 months of the data analysis period for all sites. Since the duration of the implementation period may vary from site to site, we will consider a site’s first referral to the Telemedicine Blended Model (with a PC-MHI telemedicine stopcode) as the index date with all Veterans enrolled prior to that date designated as controls and all Veterans enrolled after that date designated as intervention participants.

Figure 1: Implementation Timeline

Grant months	Identify Model	Intervention						Data Analysis
		6 months	6 months	6 months	6 months	6 months	6 months	
Site A	Implementation Planning	Implementation PDSA	Step Down					
Site B			Step Down					
Site C			Step Down					
Site D			Step Down					
Site E			Step Down					
Site F			Step Down					

Inclusion Criteria: We will sample from the patient population who screen positive on routinely administered VA MH screens (e.g., depression, alcohol, PTSD) at the 6 CBOCs, beginning 6

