CBOCs are the unit of randomization, with CBOCs randomized to an intervention start date using the stepped wedge design. A total of 6 CBOCs will participate in the study, with two CBOCs allocated to each of the 3 start dates. Randomization will be computer-generated by the statistician. A subset of potential patients (based on inclusion criteria) will be selected at each CBOC on a daily basis during the 5 measurement periods shown in Figure 1: Grant Activity Timeline (the formative evaluation control period(s), implementation, and step down period(s)).

Blinding

CBOCs and the research team will not be blinded to the intervention start dates. However, outcome assessment by independent evaluators (research assistants) will be blinded.

Statistical Analysis

The analyses will be conducted using the intention-to-treat principle, with CBOCs analyzed according to their randomized, crossover time irrespective of whether crossover took place at

the specified time. The results across the unexposed (control phase) observation periods will be compared with those across the observation periods in which the CBOCs are exposed to the Telemedicine Blended Model intervention (intervention phase). Characteristics of the patients and the CBOCs will be summarized by exposure status to examine potential selection bias or lack of balance.⁸¹ Because we have a small number (3) of randomization steps, we will compare numbers of patients analyzed, cluster (CBOC) size, CBOC characteristics and patient characteristics by randomization group. Patient-level data will be collected, with the primary analysis being patient-level.

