The CBOC-level analysis will examine the primary and secondary outcomes, summarized as the mean and standard deviation across CBOCs before and after implementation of Telemedicine Based care. At each facility, we will determine the index start date at which the first utilization of the telemedicine based service began. This will allow us to take into account the differing lengths of time it may take to implement the intervention at various CBOCs. Before this index date, patients participating in the study at that CBOC will be considered as being in the control period and those participating after the index date will be considered in the intervention phase. Analyses of before to after implementation will be conducted for continuous outcomes using linear mixed models. The interaction of intervention by CBOC will test if results differ by CBOC. We will adjust for baseline differences among CBOCs in the model.⁸²

The patient-level analysis will be a generalized linear mixed model (GLMM) which includes fixed terms for intervention (usual care referral model versus Telemedicine Based care) and time (6-month time periods for each step). The model will use random effects to model the correlation of patients within CBOCs.

The random effects model is:

$$Y_{ijl} = \mu + \beta_j + X_{ij}\theta + u_i + \varepsilon_{ijl} ; \\ u_i \sim N(0, \sigma^2_b) , \varepsilon_{ijl} \sim N(0, \sigma^2_w)$$

where β_j = fixed effect of time; $X_{ij} = 1$ if intervention, 0 otherwise; θ = intervention effect; u_i = random effect for cluster i ; ε_{ijl} = residual; $i = 1, 2, \dots, k$ clusters; $j = 1, 2, \dots, T$ time periods; and $l = 1, 2, \dots, m$ individuals.^{83, 84} In addition, we may consider adjusting the analyses to deal with lags in the intervention effect. This delayed intervention effect occurs if the intervention does not become fully effective during the step in which it is introduced.⁸⁵ If, for example, we expect the lag in the intervention effect to be 50% in the implementation step and 100% effective within 6 months, we could follow the suggestion of Hussey and Hughes of using fractional values for the treatment indicator.⁸³

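### Between a third and two-thirds of interview controls, depending on recruitment window and index date, would be followed partly after their own clinic's crossover, and no breakdown or handling of them is planned

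*Combined protocol and SAP*

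**What the plan says.** All references are to the combined protocol and SAP.

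- **Labels.** Patient Recruitment sets the index date at the site's first Telemedicine Blended referral, "with all Veterans enrolled prior to that date designated as controls and all Veterans enrolled after that date designated as intervention participants". Administrative Data groups patients by the date of their first encounter. Statistical Analysis says "Before this index date, patients participating in the study at that CBOC will be considered as being in the control period". That is unclear for a patient who participates both before and after the date. The same section also states an intention-to-treat analysis "with CBOCs analyzed according to their randomized, crossover time irrespective of whether crossover took place at" the specified time, which is a different rule from the index date.
- **Outcomes.** MCS change is measured from baseline to six months. Reach counts any 500-599 stopcode, including 534, over six months from first encounter.
- **Models.** The effectiveness model has "fixed terms for intervention (usual care referral model versus Telemedicine Based care) and time (6-month time periods for each step", plus a random clinic effect. The Reach model lists casemix factors, treatment group and, if the intra-class correlation is significant, a random intercept. It has no calendar term.
- **Recruitment window.** Patient Recruitment says "We will initiate recruitment at all sites 3 months into the first 6-month study period". Inclusion Criteria starts six months before the first implementation period. Population to be Studied starts at that period and runs 18 months. Participant Recruitment and Consent gives three years with no start date.

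**The concern.** A control who enters less than six months before the clinic's index date is followed partly in a clinic that has already switched. I call these straddling controls. For Reach the effect is mechanical: a 534 visit that such a patient makes after crossover is scored as a usual-care success. For MCS, any benefit they gain is credited to usual care.

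The nearest provisions do not cover them:

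- The optional fractional treatment indicator addresses lag after introduction: "This delayed intervention effect occurs if the intervention does not become fully effective during the step in which it is introduced".
- The optional exposure-length term ("We may include an effect modifier term in the model representing the length of the period up to the current observation") modifies the intervention effect, so it does nothing for patients coded 0.
- The as-happened analysis concerns clinics that switch off schedule: "we will include an analysis of what actually happened if the CBOCs do not crossover to the intervention at the original specified time".
- Chart review covers only Veterans enrolled after the index date.
- A 534 percentage is planned for the administrative sample, but to document uptake among those randomized to the intervention, with no breakdown for straddling controls.

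What is at stake is the reading of a null result on either hypothesis. It could mean no benefit, or benefit that reached both sides of the comparison.

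**Working it through.** **The plan's own figure.** Power Calculation inputs: t = 3, m = 18, ICC 0.01, T = 5, 20% attrition. Design effect = (1.71/1.44) x (2.97/5.333) = 0.6613. For d = 0.42 a two-sided t-test needs 180, so 180 x 0.6613 x 5 = 595, and 595/0.8 = 744, against the stated 750. The printed unadjusted total of 128 gives 423 and then 530, which does not reproduce 750; that is a separate matter. The calculation has no allowance for exposed controls.

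**Share of controls straddling.** Assumptions: uniform accrual, equal clinics, six-month steps, and implementation starting at months 6, 12 and 18. Figure 1 is partly illegible, so this timeline is rebuilt from the text. For recruitment start s and index date x, a site pair has x - s control months, of which min(6, x - s) straddle.

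| Recruitment window | Control months, on schedule | Straddling | Share | Index 3 months into step | Index at end of step |
|---|---|---|---|---|---|
| Inclusion Criteria (s = 0) | 6+12+18 = 36 | 18 | 50% | 18/45 = 40% | 18/54 = 33% |
| Patient Recruitment (s = 3) | 3+9+15 = 27 | 15 | 56% | 18/36 = 50% | 18/45 = 40% |
| Population to be Studied (s = 6) | 0+6+12 = 18 | 12 | 67% | 15/27 = 56% | 18/36 = 50% |

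The undated three-year window gives 50% or 56% if it starts at month 0 or 3.

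**Effect of the label conflict.** Take the Patient Recruitment window and an index date three months late. Under index-date labels 50% of controls straddle. Under randomized-crossover labels 9/27 = 33% do, and 9/45 = 20% of intervention-labelled patients enter before the switch.

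**MCS.** Generalised least squares with period effects and a random clinic intercept; ICC 0.01, SD 10, N = 600, Patient Recruitment window, index on schedule. Let r be the straddlers' benefit per post-crossover month relative to intervention patients, with benefit proportional to exposed time. The documents do not give r. The standard error is 1.353, and power for 4 points is Phi(4 x multiplier/1.353 - 1.96).

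| r | 0 | 0.1 | 0.25 | 0.5 | 1 |
|---|---|---|---|---|---|
| Share of effect returned | 1.0 | 0.955 | 0.89 | 0.78 | 0.55 |
| Power | 84% | 81% | 75% | 63% | 37% |

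Excluding straddling controls returns 1.0 at any r under a constant effect. Controls fall from about 225 to 100, the standard error rises to 2.15 and power falls to 46%.

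**Reach.** Linear approximation: six sites by five periods, equal cells, site effects, half of each straddling window after crossover, no secular trend. Of 12 usual-care site-periods, 6 straddle.

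| Model | Constant effect, r = 0.25 / 0.5 / 1 | 50%-then-100% phase-in, r = 0 / 0.25 / 0.5 / 1 |
|---|---|---|
| No calendar terms | 0.93 / 0.86 / 0.72 | 0.81 / 0.78 / 0.74 / 0.67 |
| Calendar terms, all patient-periods | 0.87 / 0.73 / 0.46 | 0.46 / 0.40 / 0.33 / 0.20 |
| Calendar terms, straddlers excluded | 1.0 at every r | 0.20 at every r |

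The phase-in profile is the example given in Statistical Analysis. Its average true effect over the 18 intervention site-periods is (6 x 0.5 + 12 x 1)/18 = 0.83.

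Relative standard errors: without calendar terms, 1/sqrt(2 x (0.8 + 1.2 + 1.2)) = 0.395; with them 0.732, or 1.85 times larger; with exclusion as well 1.183, a further 1.62 times.

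Without calendar terms, the intervention periods at each site are on average 15 months later than its control periods (C and D: 21 - 6; E and F: 24 - 9), so any trend over that gap enters the estimate.

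**The case against.** The best defence is that labelling by entry is a legitimate intention-to-treat rule, and that clinic crossover is not patient receipt. The straddler's positive screen comes before crossover, and a clinic may begin with a half-day-a-week pilot for two months. If r is near 0.1, the model returns 0.955 of the effect and power is still 81%. This stands. Values of r near 1 are an extreme, and a reader who infers that straddling controls were treated goes beyond the documents.

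A reader might also infer that the bias can only hide benefit. That holds only for r of zero or more. The model is staffed by reallocating existing providers. If this disrupted care for patients already in the old pathway, r would be negative, and at r = -0.25 the MCS model returns 1.11 of the effect.

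Nor do the stated windows by themselves span 33% to 67%. The dated ones give 50-67% on schedule. Reaching 33% needs a late index date, or an assumed early start for the undated window.

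Finally, excluding straddlers might look like the obvious lead analysis for Reach. It is not. It leaves A and B without controls and only one period in which both labels occur, when A and B are in their first intervention step. Under the plan's own phase-in example it returns 0.20 against a true average of 0.83.

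**Conclusion.** The gap is real and should be closed. Labels are fixed at entry, outcomes run as long as a step, and the plan neither separates out nor handles the controls whose follow-up crosses the index date. They are 50-67% of interview controls with crossover at the start of the step and 33-50% with the index date at its end, given uniform accrual and the rebuilt timeline.

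The consequence is less certain than the overlap. Dilution is the likely direction for both hypotheses. For r between 0 and 1 the MCS loss runs from none to about 45% of the effect, and the documents do not say where in that range the trial would fall. The figures are normal or linear approximations with six clusters. They do not show that the trial would fail; they show that a null result could not be interpreted without knowing the straddlers' exposure.

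**What to change.** 1. **Reach.** Add calendar-period fixed effects to the model. The Randomization section relies on aligning sites in time to control secular trends, yet the Reach model has no time term. Keep all patient-periods in the lead analysis. Report the exclusion of usual-care patient-periods that cross the index date as supportive only, and state that it is unbiased only under a constant, immediate effect and has a standard error about 1.6 times larger. State also that calendar terms cost precision and deepen dilution when straddlers are exposed or the effect phases in.
2. **Effectiveness.** Keep the planned model as primary. State one label rule, reconciling the randomized crossover time with the index date and replacing the ambiguous wording about participation. Report by site the number of straddling controls and their 534 visits after crossover, from the CDW data already to be linked. Prespecify a supportive analysis that excludes them, with the same constant-effect condition and its limits: standard error 2.15 against 1.35, power 46%, and no controls at A and B if crossover is on schedule.
3. **Recruitment.** Reconcile the four statements of the recruitment window.

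The cost is SAP wording, one tabulation, two supportive models and a less precise Reach estimate. No new data collection is needed.
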